2 RISK BENEFIT ASSESSMENT

To date, DS107 capsules has been administered to 87 healthy volunteers/patients during the course of one Phase 1 trial and one Phase 2a trial for moderate to severe AD. Up to 4g DS107 capsules was well tolerated in healthy volunteers up to 4 weeks. 2g DS107 capsules was well tolerated and safe in 51 patients with moderate to severe AD. The effect of DS107 capsules on the signs and symptoms of AD was consistently higher than placebo for all of the efficacy endpoints evaluated in this study, both investigator scores and patient scores. Following a battery of toxicology studies, and considering the endogenous nature of this molecule, it was concluded that DS107 is safe and well tolerated.

Based on both the favourable safety profile and the therapeutic potential of DS107 capsules in a disease that currently lacks effective well tolerated therapies, it can be concluded that there is a positive risk-benefit ratio for the continued investigation of DS107 capsules as a treatment for moderate to severe AD.

3 RATIONALE FOR THE STUDY

DS Biopharma (the Sponsor) showed a good safety profile for DS107 capsules for doses up to 4g, based on results of Phase I safety study.

The proof-of-concept Phase 2a study demonstrated a significant improvement in clinical efficacy measures after 8 weeks of treatment with DS107 capsules in patients with AD. Importantly there was a significant improvement in the number of moderate AD patients who achieved the primary endpoint compared to placebo treated patients. There was a similar efficacy observed in severe/very severe AD patients, however, the sample size was deemed too small to determine the statistical significance.

The two previous clinical studies indicate that DS107 capsules is well tolerated and safe in both healthy patients and patients with moderate to severe AD. The Phase 2a study highlights the efficacy of DS107 capsules and indicates that further efficacy could be obtained by optimizing the dosing regime and/or concentration. Therefore, the goal for this dose-finding study is to examine the efficacy of 2g DS107 capsules OD and 1g DS107 capsules OD for a treatment period of 8 weeks in patients with moderate to severe AD.

The design of the current study is a randomised, placebo-controlled, and double-blind parallel group comparison in which the efficacy and safety of an 8 week treatment with DS107 capsules is assessed in patients with moderate to severe AD. The design of the study minimises bias during the safety and efficacy assessments.

The novel mechanism of action and safety profile of DS107 capsules offer a potential benefit to AD patients and would represent a new class of medicine for this disease.

Based on the afore mentioned preclinical studies demonstrating the efficacy of DS107 in animal models of AD, the positive signals in the Phase 2a study in patients there is a clear rationale for the further development of DS107 capsules as a treatment for patients with moderate to severe AD.

4 STUDY OBJECTIVES

Efficacy Objective:

- To compare the efficacy of orally administered DS107 versus placebo, in the treatment of adult patients with moderate to severe AD.

Safety Objective:

- To assess the safety of orally administered DS107 versus placebo, in adult patients with moderate to severe AD.

5 STUDY ENDPOINTS

5.1 Primary Endpoint

- Proportion of patients achieving an Investigator's Global Assessment (IGA) of 0 (clear) or 1 (almost clear) and a decrease of at least 2 points in IGA in treated population compared to placebo population at Week 8.

5.2 Secondary Endpoints

- Proportion of patients achieving an IGA score of 0 (clear) or 1 (almost clear) and a decrease of at least 2 points in IGA in treated population compared to placebo population from baseline to Week 2, 4, 6 and 10.
- Proportion of patients achieving a decrease of at least 2 points in IGA in treated population compared to placebo population from baseline to Week 2, 4, 6, 8 and 10.
- Change from baseline in Eczema Area and Severity Index (EASI) in treated population compared to placebo population at Week 2, 4, 6, 8 and 10.
- Change from baseline in Numeric Rating Scale (NRS) for Pruritus in treated population compared to placebo population at Week 2, 4, 6, 8 and 10.

5.3 Exploratory Endpoints

- Change from baseline in the Dermatology Life Quality Index (DLQI) score in treated population compared to placebo population at Week 2, 4, 6, 8 and 10.
- Change from baseline in the Patient Orientated Eczema Measure (POEM) score in treated population compared to placebo population at Week 2, 4, 6, 8 and 10.
- Change from baseline in the Patient Global Impression of Severity (PGI-S) score in treated population compared to placebo population at Week 2, 4, 6, 8 and 10.
- Change from baseline in the Patient Global Impression of Change (PGI-C) score in treated population compared to placebo population at Week 2, 4, 6, 8 and 10.
- Plasma DGLA concentrations in treated population compared to placebo population at Baseline/Day 0, Week 4, Week 8 and Week 10 of (samples to be retained and analysed for the potential analysis at a later date).
- Determination of AD biomarkers at Baseline/Day 0, and Week 8 (samples to be retained and analysed at a later date for the potential analysis).

6 STUDY DESIGN

6.1 General

[figure not shown]
This is a randomised, placebo-controlled, double-blind, parallel group, multi-centre 3-arm Phase 2b study to investigate the efficacy of orally administered DS107 and the dose-response relationship between DS107 capsules and placebo in AD patients 18 years and older.

It is planned that at least 300 patients with at least 100 patients per treatment group, suffering from moderate to severe AD will be included in this study. All patients will sign an informed consent and undergo screening for study eligibility. Patients will be randomized (1:1:1) at baseline visit to either receive 2g DS107, 1g DS107 or placebo once daily for 8 weeks.

Patients will come to the clinic on 7 occasions: at Screening/Visit 1, Baseline/Visit 2, Week 2/Visit 3, Week 4/Visit 4, Week 6/Visit 5 and /Week 8/Visit 6 (end of treatment) and Week 10/Visit 7 (follow-up). Early termination visits will be recorded for patients who withdraw from the study early. All patients will exit the study at the Week 10 visit. At the screening visit, after giving informed consent to participate, patients will be assessed using the screening examinations. Patients who meet the inclusion criteria and who do not meet the exclusion criteria will be enrolled.

Unlike other oral treatments for AD (e.g. steroids) a treatment effect of DS107 capsules is not immediately expected to occur after start of treatment, but to increase constantly over time reaching its maximum effect within a time period over 4-6 weeks. Therefore, every effort should be undertaken to continue treatment with DS107 at least for 4 weeks to determine the efficacy of DS107. Patients not willing to continue to participate in the study due to the apparent lack of efficacy within the first 4 weeks of treatment therefore should be replaced. A schematic diagram of the overall timeframe of the study is given in Figure 2.

Figure 2: Study Outline

Once patients are enrolled on the study they will be restricted from using any other treatment for AD, with the exception of emollients, as defined in section 9.2.11. Any medication (prescription as well as over the counter (OTC) drugs) or therapeutic intervention deemed necessary for the patient, and which in the opinion of the Investigator do not interfere with the safety and efficacy evaluations, may be continued unless they are included in the list of ‘Concomitant Medications’ (Section 9.2.11).

Before the comparative treatment period can commence, patients will return to the site for a baseline assessment of their disease and eligible patients will be randomly allocated to one of the three parallel group treatment regimens in a 1:1:1 randomization:

- Treatment group A: 1g DS107 (2 DS107 capsules and 2 placebo capsules) administered once-daily for 8 weeks
- Treatment group B: 2g DS107 (4 DS107 capsules) administered once-daily for 8 weeks
- Treatment group C: Placebo (4 placebo capsules) orally administered once-daily for 8 weeks

To maintain the double-blind conditions, DS107 capsules and Placebo will be identical in appearance.

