12.3 Estimation of Sample Size

In the Phase 2a trial, IGA response rates of 21.6% and 11.8% were observed for DS107 and Placebo respectively. Assuming these rates and a significance of 5%, 300 evaluable patients (100 patients per treatment arm) will yield 45% power for comparisons between the active doses and placebo in this study.

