2.2.8 Statistical Hypotheses

The overall null hypothesis (H_0) for each analysis is the equality of the means for the three treatment groups. A global test will be performed across all three treatment groups to allow for a penalty-free comparison of the comparison of the 1g and 2g concentrations against the placebo control. In the event of a global difference (two-sided $p < 0.05$), then the between-treatment comparison of the 2g active treatment group to placebo is performed. If significant (two-sided $p < 0.05$) then the between-treatment comparison of the 1 g active treatment group to the placebo is performed; otherwise the p-values will be regarded as descriptive statistics. The Type I error rate is controlled for by the hierarchical approach. All testing will be two-sided; global tests will be performed at the 0.05 level. Testing between the 2 active groups will be considered descriptive statistics.

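### The global three-group test that SAP 2.2.8 puts ahead of 2g v placebo is not penalty-free: it costs about 3 to 13 points of power, adds no needed error control, and is absent from SAP 2.1

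*Protocol*

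**What the plan says.** **The testing order.** SAP 2.2.8 (Statistical Hypotheses) says: "A global test will be performed across all three treatment groups". Only if that test gives two-sided p < 0.05 is 2g compared with placebo, and only if 2g succeeds is 1g compared with placebo. Otherwise the p-values are descriptive. The section calls the arrangement penalty-free, yet credits control of Type I error to the hierarchy. On the two doses it says: "Testing between the 2 active groups will be considered descriptive statistics".

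**Two other accounts of it.** SAP 2.1 (General Considerations) gives the hierarchy as 2g v placebo at 0.05, then 1g v placebo at 0.05, with no global test first. The protocol synopsis (Statistical Analysis) says that no adjustment for multiplicity will be made.

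**Dose-response.** Protocol 6.1 says the study investigates "the dose-response relationship between DS107 capsules and placebo". Protocol 3 says "the goal for this dose-finding study is to examine the efficacy of 2g DS107 capsules OD and 1g DS107 capsules OD". The formal efficacy objective in Protocol 4 is narrower: "To compare the efficacy of orally administered DS107 versus placebo, in the treatment of adult patients with moderate to severe AD".

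**Model.** The code in SAP 2.2.12.1 has treatment arm as a class variable, and a SLICE statement that requests differences between arms and confidence limits at each visit.

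**The concern.** A global test of three arms has two degrees of freedom and takes no account of dose order. If 2g v placebo may be tested only after it, the main comparison has to pass two tests. A trial in which 2g beats placebo at p < 0.05 can still fail the gate, and its 2g result then becomes descriptive.

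Neither sample-size statement allows for this. Protocol 12.3 and SAP 2.2.9 both size the trial for one active dose against placebo. Because SAP 2.1 and 2.2.8 differ, two analysts could also follow the SAP correctly and disagree on whether 2g had formally succeeded.

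**Working it through.** **1. Inputs**
- Protocol 12.3: "IGA response rates of 21.6% and 11.8% were observed for DS107 and Placebo respectively", and "300 evaluable patients (100 patients per treatment arm) will yield 45% power for comparisons between the active doses and placebo".
- SAP 2.2.9: placebo 10%, difference 15 points (so 25% on active), 100 per arm. SAP 2.2.10 names at least 80% power and two-sided 5% error as the aim of the interim resizing.
- Assumption: the 1g rate. Neither document gives it, so it runs from the placebo rate to the 2g rate.

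**2. The plan's own figures**

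Power = Φ[(|p₂ − p₀| − 1.96·SE₀)/SE₁], where SE₀ = √[2p̄(1 − p̄)/n], p̄ is the mean of the two rates, and SE₁ = √[(p₂(1 − p₂) + p₀(1 − p₀))/n].
- Protocol: SE₀ = 0.0527, SE₁ = 0.0523, (0.098 − 1.96 × 0.0527)/0.0523 = −0.10, power **45.9%** (stated: 45%).
- SAP: 10% v 25% at 100 per arm gives **80.2%**, and 100 per arm is the size needed for 80%.

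Both reproduce with no gate.

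**3. Why the gate costs power**

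The noncentrality of the global chi-square is λ = n·Σ(pᵢ − p̄)²/[p̄(1 − p̄)], with p̄ now the mean over three arms. With 1g midway at protocol rates (11.8/16.7/21.6%):

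λ = 100 × (2 × 0.049²)/(0.167 × 0.833) = 3.45.

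Here the whole departure from equality lies in 2g minus placebo, so a one-degree-of-freedom test of that difference, using the three-arm pooled variance, has the same λ. The one-df test needs a statistic above 3.84 and the global test needs 5.99. Power is about 46% for the first and 36% for the second. At SAP rates (10/17.5/25%), λ = 7.79 and the figures are about 80% and 71%.

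**4. Power for 2g v placebo, with and without the gate**

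Simulation: 400,000 trials per row, three binomial arms of 100, Pearson chi-square for the global test, pooled z test for 2g v placebo, two-sided 5%.

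| Rates | 1g rate | No gate | With gate | Loss (points) |
|---|---|---|---|---|
| Protocol | = placebo | 46.8% | 39.6% | 7.2 |
| Protocol | midway | 46.7% | 33.8% | 12.9 |
| Protocol | 75% of 2g effect | 46.8% | 34.3% | 12.5 |
| Protocol | = 2g | 46.7% | 36.5% | 10.2 |
| SAP | = placebo | 81.6% | 78.4% | 3.2 |
| SAP | midway | 81.6% | 70.6% | 11.0 |
| SAP | 75% of 2g effect | 81.6% | 72.4% | 9.2 |
| SAP | = 2g | 81.6% | 76.2% | 5.4 |

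The simulated ungated power is 1 to 2 points above the formula in step 2. With 1g midway at protocol rates, (46.7 − 33.8)/46.7 = 28% of trials with a significant 2g result would fail the gate.

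**5. Error rate**

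With all three rates equal at 11.8%, 2g is declared different from placebo in 2.5% of trials with the gate and 5.2% without it (the excess over 5% comes from the normal approximation). The gate leaves about half of the 5% unused. It is not needed for control: in a fixed sequence, 1g is tested only after 2g succeeds, each at 5%, so the chance of any false claim against placebo stays at 5%.

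**6. Sample size implied by the gate**

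With 1g midway, 80% power on the global test alone needs about 124 per arm at SAP rates and about 280 at protocol rates, against 100 and 227 for 2g v placebo.

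**7. What 2g v 1g can show**

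At 21.6% v 16.7%, SE₁ = √[(0.216 × 0.784 + 0.167 × 0.833)/100] = 0.0555. The 95% confidence half-width is 1.96 × 0.0555 = 10.9 points around a difference of 4.9, and power is about 14% by the formula in step 2 (about 15% simulated). At 25% v 17.5%, the half-width is 11.3 points and power about 25%.

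**The case against.** **A global test before pairwise tests is a recognised procedure.** With three arms, a significant global test followed by unadjusted pairwise tests does control the familywise error, and that may be what penalty-free meant. But that method then lets either dose be tested in either order. SAP 2.2.8 adds a fixed order as well, and so pays for two protections where one is enough.

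**The interim may restore power.** SAP 2.2.10 allows the sample size to rise. That could offset the loss, but only if the resizing is calculated for the gated procedure, which the SAP does not say.

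**The gate may not be intended.** SAP 2.1 omits it and the protocol plans no adjustment. This is correct, and it is part of the point: the documents do not settle which rule applies.

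**A stronger reading.** A reader might infer that dose-response goes unanalysed and that a linear contrast (−1, 0, 1) should replace the global test. The documents do not support this.
- Dose-response appears in the design description, not in the formal objective. The dose-finding sentence in Protocol 3 goes on to speak of efficacy at each dose.
- Dose order is used: the sequence starts at the higher dose.
- The SLICE statement already yields arm-level estimates and the 2g v 1g difference with confidence limits.
- With equal arms at 0, 1 and 2 g, the contrast gives 1g no weight. From the planned class-variable model it is the 2g v placebo comparison itself. Rates of 10/0/25% and 10/40/25% both give 15 points, so it says nothing about shape.
- A separate trend test that pools variance over three arms reaches the same decision as 2g v placebo in 96-98% of simulated trials. If 1g equals 2g it is weaker than the global test: 43.2% v 45.3% at protocol rates, 77.7% v 83.3% at SAP rates. As a gate it still loses to no gate there: 43.1% v 46.7%, and 77.6% v 81.6%.

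**Conclusion.** The concern holds as a point about the gate. SAP 2.2.8 is wrong to call the global test penalty-free, and it conflicts with SAP 2.1. The gate costs 2g v placebo 7 to 13 points of power at protocol rates and 3 to 11 at SAP rates. At the SAP's own rates, gated power is below 80% for every 1g rate examined. No familywise protection would be lost by removing it.

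The figures assume an unadjusted binary comparison at Week 8, 100 evaluable patients per arm, no effect of the interim analysis, and a 1g rate between the placebo and 2g rates. The planned repeated-measures model with covariates would shift the levels somewhat.

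The point does not extend to a missing dose-response test. Keeping 2g v 1g descriptive is reasonable at its low power. What is worth adding is a commitment to report it as an estimate.

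**What to change.** 1. In SAP 2.2.8, remove the global test as a condition for 2g v placebo (it may stay as a descriptive result). State the sequence as 2g v placebo, then 1g v placebo, each at two-sided 0.05, and delete the penalty-free wording.
2. Make SAP 2.1 and 2.2.8 say the same thing, and reconcile both with the protocol synopsis, for example by recording that the SAP's fixed sequence supersedes the no-adjustment statement.
3. State that any interim resizing is calculated for the testing procedure finally adopted.
4. For the dose-response aim in Protocol 6.1, name the Week 8 comparison of 2g with 1g and its 95% confidence interval as a reported estimate, not a test. The SLICE statement gives it on the logit scale, so say whether a difference in percentage points will be shown too. Do not present a (−1, 0, 1) contrast as a dose-response analysis.

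The cost is a few lines of SAP text, settled before unblinding. Design, data collection and the primary model are unchanged. Items 1 and 2 recover the power at no loss of error control.

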7.6 Patient Replacement

Patients who are withdrawn from the study due to an adverse event will not be replaced. Patients who are withdrawn for other reasons (such as lost to follow up, personal reasons) may be replaced.

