11.3 Differentiation of Treatment Failure and AE

Please note, that the lack of improvement of the symptoms of AD is not an AE and should be reported as treatment failure.

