12.7 Analysis Populations

Enrolled Population

The Enrolled Population consists of all patients who sign informed consent.

Screen Failures

Screen Failures are patients from the Enrolled Population who do not meet the eligibility requirements and are withdrawn from the study prior to Randomisation.

Randomised Population

The Randomised Population consists of all patients who are randomised to the study.

Safety Analysis Set (SAS)

The Safety Analysis Set (SAS) consists of all patients who received at least one dose of the medication. SAF is the analysis population for all safety endpoints. Analysis will be done according to the actual treatment patients received.

Full Analysis Set (FAS)

The Full Analysis Set (FAS) consists of all patients who are randomised to the study and received at least one dose of study medication. FAS is the primary analysis population for efficacy endpoints. Analysis will be done according to the treatment patients were randomised to.

Per Protocol Set (PPS)

The Per Protocol Set (PPS) is the subset of FAS who completed the study without any major violations. Protocol violations will be assessed for each patient in a blinded fashion prior to database lock at a Blind Data Review Meeting (BDRM), and the PPS will also be finalised

during this meeting. PPS is a supportive analysis population for efficacy endpoints. Analysis will be done according to the treatment patients were randomised to.

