2.2.4 Study Populations for Analysis

2.2.4.1 Full Analysis Set (FAS)

The FAS consists of all patients who are randomized to the study and received at least one dose of study medication. FAS is the primary analysis population for efficacy endpoints. Analysis will be done according to the treatment patients were randomized to.

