2.2.4.3 Per-Protocol Analysis Set (PPS)

The PPS is the subset of FAS who completed the study without any major violations. Protocol violations will be assessed for each patient in a blinded fashion prior to database lock at a Blind Data Review Meeting (BDRM), and the PPS will also be finalized during this meeting. PPS is a supportive analysis population for the primary efficacy endpoint. Analysis will be done according to the treatment that patients were randomized to.

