2.2.6 Methods for Handling Missing Data

PROC GENMOD will be used to account for any missing data and early withdrawal for FAS.

The GENMOD procedure will estimate the working correlation from data containing both types of missing values by using the *all available pairs* method, in which all non-missing pairs of data are used in the moment estimators of the working correlation parameters. The resulting covariances and standard errors are valid under the missing completely at random (MCAR) assumption.

A sensitivity analysis will be performed for the Week 8/Exit outcome under the missing at not random (MNAR) assumption for the primary efficacy analyses using the FAS. An extreme analysis will be used to identify the possible outcome considering two scenarios: An extreme analysis will be used to identify the possible outcome considering the worst case for both active treatments and best case for vehicle (Scenario 1) and then the reverse (Scenario 2). If any extreme cases result in statistical significance, then the maximum degree of relaxation per

treatment group still reaching statistical significance will be displayed for each scenario. A two-sided Fisher Exact Test will be utilized for these analyses.

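### Replacement after early withdrawal for lack of efficacy is instructed inconsistently, and the SAP does not say how these treatment failures count at Week 8

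*Protocol*

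**What the plan says.** **Replacement.**

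- Protocol 6.1 explains that the effect of DS107 is expected to build up over 4-6 weeks. It then says that patients not willing to stay in the study "due to the apparent lack of efficacy within the first 4 weeks of treatment therefore should be replaced".
- Protocol 7.6 is permissive: "Patients who are withdrawn for other reasons (such as lost to follow up, personal reasons) may be replaced". Lack of efficacy is not among its examples. It also says: "Patients who are withdrawn from the study due to an adverse event will not be replaced".
- Protocol 7.5.2 lists lack of efficacy among the reasons for stopping product while visits and efficacy evaluations continue.

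**Analysis sets.**

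- Protocol 12.7: "The Full Analysis Set (FAS) consists of all patients who are randomised to the study and received at least one dose of study medication". SAP 2.2.4.1 uses the same definition and adds: "FAS is the primary analysis population for efficacy endpoints".
- SAP 2.2.4.3, on the per-protocol set: "The PPS is the subset of FAS who completed the study without any major violations". SAP 2.2.12.1 repeats the primary analysis on that set.

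**Missing Week 8 values.**

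- SAP 2.2.6 fits PROC GENMOD to the available data and says: "The resulting covariances and standard errors are valid under the missing completely at random (MCAR) assumption". Protocol 12.9.2 assumes MAR instead.
- SAP Appendix A, item 4.2, bases percentages on subjects with non-missing data unless otherwise noted.
- Protocol 7.5 asks early leavers to attend for the Week 8 assessments, which include IGA (8.2.7). SAP 2.2.5 lets Visit 6 fall early for them, and SAP 2.2.6 speaks of a Week 8/Exit outcome. SAP 2.2.12.2, however, lists the last treatment visit as a time point separate from Week 8.

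**The concern.** Leaving because the treatment does not work is itself an outcome. In the context of AE reporting, Protocol 11.3 says that "the lack of improvement of the symptoms of AD is not an AE and should be reported as treatment failure". A rule that replaces patients for this reason, but never for an adverse event, makes the composition of the completing sample depend on why people left.

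FAS membership alone does not give such a patient a Week 8 result. If the value is missing, an analysis that needs missingness to be unrelated to outcome is applied to patients who left because of their outcome. The Week 8 response rates are then too high in each arm, by an amount that depends on how many failures that arm lost.

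Two decisions depend on these rates or counts. Protocol 12.3 bases power on 300 evaluable patients without defining evaluable. SAP 2.2.10 uses the data after 150 patients reach Week 8/Exit to update the primary-endpoint assumptions, adjust the sample size and judge futility.

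**Working it through.** **Inputs.** From Protocol 12.3: response rates of 21.6% (DS107) and 11.8% (placebo), 100 evaluable patients per arm, 5% significance, 45% power. The protocol synopsis makes tests two-sided. Neither document gives a rate of early exit for lack of efficacy, so the share d is assumed, from 5% to 20%.

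**1. The plan's own figure.** Pooled normal approximation for two proportions:

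- Mean rate (0.216 + 0.118)/2 = 0.167. Null SE = sqrt(2 × 0.167 × 0.833/100) = 0.0527.
- Alternative SE = sqrt((0.216 × 0.784 + 0.118 × 0.882)/100) = 0.0523.
- Power = Φ((0.098 - 1.96 × 0.0527)/0.0523) = Φ(-0.103) = 45.9%. The stated 45% reproduces.

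**2. Observed rate when leavers have no Week 8 value.** Suppose a share d of an arm leaves, all would have been non-responders, and none has a Week 8 value. The observed rate is then p/(1-d). This approximates what the repeated-measures model would return.

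| Assumed d, placebo / active | Placebo | Active | Difference (points) |
|---|---|---|---|
| 0 / 0 | 11.8% | 21.6% | 9.8 |
| 5% / 5% | 12.4% | 22.7% | 10.3 |
| 10% / 10% | 0.118/0.90 = 13.1% | 0.216/0.90 = 24.0% | 10.9 |
| 20% / 20% | 0.118/0.80 = 14.8% | 0.216/0.80 = 27.0% | 12.3 |
| 20% / 10% | 14.8% | 24.0% | 9.3 |
| 10% / 20% | 13.1% | 27.0% | 13.9 |

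Differences are taken from unrounded rates (for example 24.00 - 14.75 = 9.25).

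**3. What replacement adds.** Take placebo at d = 10%.

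- Without replacement: 100 randomised, 90 observed, 11.8 expected responders. 11.8/90 = 13.1%.
- With replacement until 100 are observed: 100/0.90 = 111 randomised, 13.1 expected responders. 13.1/100 = 13.1%.
- Counting everyone randomised, with leavers as non-responders: 13.1/111 = 11.8%.

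The inflation is the same with or without replacement and disappears once leavers are counted. Replacement restores the observed n: with d = 10% in both arms, power on the inflated rates is 50.8% with it and 46.7% without.

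**4. Where leavers drop out.** They leave the per-protocol set by definition, since it holds completers only. They leave percentages based on non-missing data. They leave the primary model only if the early-termination IGA is not used as Week 8. SAP 2.2.5 and the Week 8/Exit wording in 2.2.6 suggest it is used; the separate last-treatment-visit analysis in 2.2.12.2 suggests it is not.

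**5. Whether another planned analysis closes the gap.** The extreme-case analysis in SAP 2.2.6 sets worst case in the active arms against best case in the control arm, then reverses them, so each scenario counts some missing patients as responders. The jump-to-reference analysis in Protocol 12.9.2 imputes placebo-like outcomes, so a known failure can be imputed as a responder; the SAP does not carry it over. Neither counts lack-of-efficacy leavers as non-responders in all arms.

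**The case against.** A reader might infer from 6.1 that failures are swapped for patients who stay, and that this raises the response rates or favours DS107. The documents do not support that. The FAS keeps everyone randomised and dosed, and no section removes a replaced patient or lets a replacement inherit the leaver's arm. Step 3 shows that the expected rate is unchanged by replacement. Swapping describes only the per-protocol set, which is supportive. Nor is there a known advantage to the drug: if placebo loses more failures, the difference shrinks.

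The plan also tries to obtain the missing data. Early leavers are asked for the Week 8 assessments, 7.5.2 foresees continued efficacy evaluation, and both documents contain a missing-data sensitivity analysis. If the early-termination IGA does enter the model as Visit 6, most of these patients would appear as observed non-responders and little bias would remain.

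Finally, counting leavers as non-responders is a choice of estimand. Protocol 12.9.2 deliberately targets the effect under full adherence.

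Most of this stands and limits the point. What it does not answer is that the visit is only requested, that the SAP gives mixed signals on whether its IGA serves as Week 8, and that the SAP's primary analysis rests on MCAR, which an exit for lack of efficacy violates.

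**Conclusion.** The point holds in a limited form. Sections 6.1, 7.6 and 7.5.2 of the protocol give different instructions for the same patient and must be reconciled. Replacement by itself does not bias the FAS response rates; it fills the evaluable count and the per-protocol set with patients who stay, so a sample selected on outcome looks complete.

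The bias, if it arises, comes from Week 8 values that are missing because of lack of efficacy. With 5% to 20% of each arm lost equally, rates rise by 0.6 to 3.0 points on placebo and 1.1 to 5.4 on active. Unequal loss moves the 9.8-point difference to 9.3 or to 13.9 in the two cases shown, so its direction cannot be stated in advance.

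These sizes rest on three assumptions: the exit shares, that every leaver would have been a non-responder, and that replacements come from the same population.

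**What to change.** 1. In SAP 2.2.6 and 2.2.12.1, count any FAS patient who withdraws for lack of efficacy as a Week 8 non-responder, in every arm and whether or not replaced. State that the early-termination IGA does not override this. Say whether the rule covers patients who stop product under 7.5.2 but attend Week 8.
2. Remove the outcome-based replacement sentence from Protocol 6.1 or reconcile it with 7.6 and 7.5.2. State that any replacement is a newly randomised addition and that the replaced patient remains in the FAS. Removing the sentence without item 1 would leave the expected FAS rates unchanged.
3. Align the missing-data text in Protocol 12.9.2 with item 1, since it changes what is estimated for these patients.

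The cost is wording. Protocol 7.5 already has the reason for withdrawal recorded, so no new data are needed. Stated response rates will be slightly lower, and the primary analysis departs a little from the available-data approach. With 100 randomised per arm, no replacement and d = 10% in both arms, power is 45.9% when leavers are counted, against 46.7% when they are missing.
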